5 STUDY ASSESSMENTS AND PROCEDURES

5.1 Flow Chart/Time and Events Schedule

Study assessments and procedures are presented in Table 5.1-1, Table 5.1-2, and Table 5.1-3. In limited instances, scheduled events can occur outside of the indicated timeframes, but BMS should be notified.

Procedure ^a	Screening Visit D-28 to D-1	C1D1	C1D2	C1D4 ^b	C1D8	C1D15	Notes		
Eligibility Assessments									
Informed Consent	Х						A subject is considered enrolled only when a protocol-specific informed consent is signed. In BMS-986183 dose expansion (Part 2) and BMS-986183 and nivolumab dose expansion (Part 4), if allowed by institutional practices, sites are encouraged to use a prescreening consent for the GPC-3-expressing tumor analysis. Other screening procedures should not be performed before the GPC-3-expressing tumor analysis is available for the determination of subject eligibility. Refer to Section 3.1 for additional details on screening.		
IRT Assignment	Х								
Inclusion/Exclusion Criteria	Х						Assessed during screening period. All inclusion/exclusion criteria must be met for subjects to participate in the study.		
ECOG	Х	X					Refer to Appendix 5 and Section 3.3.1. For Screening, must be within 14 days prior to treatment assignment.		
Medical History	Х						Include any toxicities or allergy related to previous treatments, smoking history, asthma, chronic obstructive pulmonary disease, history of hepatic encephalopathy. Includes detailed medical history of potential risk factors for potential events such as pulmonary-related events, cardiovascular history, neurological toxicity, infusion or hypersensitivity reactions, and smoking history. Ensure documentation of hepatitis risk factors.		
History of Alcohol use	Х								
Child-Pugh Score	Х	Χ					See Appendix 4 for scale		
Prior Treatments	X						Including prior cancer treatment regimens		
Safety Assessments									
Full PE	X	X					For Screening, must be within 14 days prior to treatment assignment. If the screening full PE is performed within 24 hours prior to dosing on Day 1, then a single exam may count as both the screening and predose evaluation.		

Table 5.1-1:Screening and Cycle 1 Procedural Outline (CA015003)

Procedure ^a	Screening Visit D-28 to D-1	C1D1	C1D2	C1D4 ^b	C1D8	C1D15	Notes
Targeted PE					X	X	Targeted examination must include at a minimum the following body systems, performed within 72 hours prior to dosing: cardiovascular, gastrointestinal, pulmonary, and skin. The targeted examination also includes signs and symptoms of peripheral neuropathy.
Physical Measurements	Х	X					Height (screening only), weight (for Screening, must be within 14 days prior to treatment assignment).
Vital Signs ^c	Х	X			X	X	Body temperature, blood pressure, and heart rate (for Screening, must be within 14 days prior to treatment assignment).
ECGs	Х	X	X		X		ECGs should be recorded after the subject has been supine for at least 5 minutes. ECGs will be taken prior to dosing. For ALL subjects in BMS-986183 dose escalation (Part 1) and at least 20 subjects in BMS-986183 dose expansion (Part 2): Time matched for PK; triplicate ECG evaluations at C1D1 predose and EOI, C1D2 (24 hours post dose), and C1D8 (168 hours post dose) QTcF assessment > 480 msec must be confirmed on repeat ECG.
ECHO or MUGA	Х						Must include a quantitative assessment of left ventricular ejection fraction and utilize the same modality for any subsequent assessments. ECHO/MUGA may be assessed up to 72 hours prior to the first dose.
Laboratory Tests	Х	X	x	x	x	x	Screening laboratory values should be obtained within 14 days prior to the start of study drug. If the screening laboratory tests are performed within 72 hours prior to dosing on Day 1 then a single exam may count as both the screening and predose evaluation. Urine - screening only, unless clinically indicated FSH - screening only, if needed to document post-menopausal status C1D4: CBC and LFT only, collection to be time-matched with PK collection See Section 5.3.2.

Table 5.1-1:Screening and Cycle 1 Procedural Outline (CA015003)

Table 5.1-1:	Screening and Cycle 1	Procedural Outline (CA015003)
--------------	-----------------------	-------------------------------

Procedure ^a	Screening Visit D-28 to D-1	C1D1	C1D2	C1D4 ^b	C1D8	C1D15	Notes
Thyroid Panel including TSH, free T3, and free T4	Х						Required for BMS-986183 and nivolumab combination therapy only. See Section 5.3.2. Free T3 and free T4 are required at screening and then taken reflexively if TSH is abnormal.
Coagulation Panel	Х	Х			Х		See Section 5.3.2.
Serology (Hepatitis B, Hepatitis C)	х						HBV DNA viral load (PCR), HCV RNA (HCV antibody testing with HCV RNA reflex), hepatitis D antibody, HBV core antibody HBeAg, HBeAb, HBsAb, and HBsAg.
Viral biomarkers (for HCV and HBV)		Х					For HCV infected, HCV RNA on treatment For HBV infected, HBV DNA on treatment
Troponin T or I	Х	Х			Х	Х	The same evaluation (assay) must be performed throughout the study
Pregnancy Test	Х	Х					For WOCBP only; see Section 5.3.2
Whole blood sample for ADME		Х					See Section 5.7.3
PK and Immunogenicity Assessments S	ee Section 5.5.						
Biomarker Assessments See Section 5.6.							
Tumor Sample	Х						See Section 3.3.1.
Tumor Assessment Tumor Imaging (See Section 5.3.1)	х						Baseline must be within approximately 30 days of C1D1 Scans must be de-identified. See Section 5.3.1.
Concomitant Treatments		X	X	X	X	X	Medications administered within 4 weeks of dosing and all anti-viral medications taken for any length of treatment through 60 days post-study drug discontinuation for BMS-986183 dose escalation (Part 1) and BMS-986183 dose expansion (Part 2) and for 100 days after the last dose of study drug for BMS-986183 and nivolumab dose escalation (Part 3) and BMS-986183 and nivolumab dose expansion (Part 4).

Procedure ^a	Screening Visit D-28 to D-1	C1D1	C1D2	C1D4 ^b	C1D8	C1D15	Notes
Adverse Event Reporting		•					
Clinical Complaints	Х						Clinical complaints related to the disease under study must be collected within 14 days of the first dose of study drug.
Monitor for Nonserious Adverse Events							BMS-986183 dose escalation (Part 1) and BMS-986183 dose expansion (Part 2): From first dose of study drug until a total of 60 days post discontinuation of dosing or subject's participation in the study if the last scheduled visit occurs at a later time.
		X	Х	X	Х	Х	BMS-986183 and nivolumab dose escalation (Part 3) and BMS-986183 and nivolumab dose expansion (Part 4): From first dose of study drug until a total of 100 days post discontinuation of dosing or subject's participation in the study if the last scheduled visit occurs at a later time.
							See Section 5.3.
Monitor for SAEs							BMS-986183 dose escalation (Part 1) and BMS-986183 dose expansion (Part 2): From the time of consent until a total of 60 days post discontinuation of dosing.
	Х	Х	Х	Х	Х	Х	BMS-986183 and nivolumab dose escalation (Part 3) and BMS-986183 and nivolumab dose expansion (Part 4): From the time of consent until a total of 100 days post discontinuation of dosing. See Section 5.3.
Clinical Drug Supplies		l		l	l		
Dose Level Assignment	Х						At the completion of screening procedures and eligibility determined
Dispense Study Drug		v					Those supplied by BMS; the start and stop time of the study drug infusion should be documented (start of drug infusion = 0 hour). Subjects in BMS-986183 dose escalation (Part 1) and BMS-986183 dose expansion (Part 2) receive BMS 026183 monotherapy
		X					Subjects in BMS-986183 and nivolumab dose escalation (Part 3) and BMS-986183 and nivolumab dose expansion (Part 4) receive BMS-986183 and nivolumab combination therapy.

Table 5.1-1:Screening and Cycle 1 Procedural Outline (CA015003)

- ^a In the event that multiple procedures are required at a single timepoint, the ECG may be obtained up to 15 minutes earlier, vital signs may be obtained up to 10 minutes earlier or later, and clinical laboratory sample may be obtained up to 5 minutes earlier than the nominal PK timepoint, ensuring the PK samples can be collected on time.
- ^b C1D4 visit: ± 1 day.
- ^c During C1: vital signs will be obtained before the BMS-986183 infusion and then every 15 minutes (\pm 5 minutes) until 60 minutes after completion of the infusion. After C1 vital signs may be obtained predose, every 30 minutes (\pm 10 minutes) until 30 minutes following completion of the infusion. If any vital sign is abnormal at the final check, the subject must be observed further for a period of time, as clinically indicated. The start and stop time of the study drug infusion should be documented (start of drug infusion = 0 hour).
- C = cycle, D = day; EOI = end of infusion; HBeAb = hepatitis B e antibody; HBsAb = hepatitis B surface antibody; PCR = polymerase chain reaction; T3 = triiodothyronine; T4 = thyroxine; TSH = thyroid stimulating hormones.

Procedure ^a	C	2 and	C3		C4					ЕОТ	Follow- up (30 and 60 Days After Last Dose)	Follow- up (100 Days After Last Dose) ^C	Survival Follow-up ^d	Notes
	D1	D8	D15	D1	D2	D4 ^e	D8	D15	D1		(± 5 days)	(± 10 days)	(± 2 weeks)	
Safety Assessments														
Child-Pugh Score	Х			Х					Х	Х	Х	Х		See Appendix 4 for scale
Full PE										Х				
Targeted PE	Х	Х	Х	Х					Х		Х	Х		See note in Table 5.1-1.
Physical Measurements	Х			Х					Х	Х	Х	Х		Weight only
Vital Signs ^f	Х	Х	Х	X					Х	Х	Х	X		See note in Table 5.1-1.
ECGs	x			x	x		х		Х	Х	Х	X		See note in Table 5.1-1. ALL subjects in BMS-986183 dose escalation (Part 1) and at least 20 subjects in BMS-986183 dose expansion (Part 2) will have time matched for PK; triplicate evaluations at C4D1 predose and EOI, C4D2 (24 hour post dose), and C4D8 (168 hours post dose)
Laboratory Tests	x	X	X	x		X	x	x	Х	Х	Х	X		See note in Table 5.1-1 and Section 5.3.2. C4D4 (CBC only) collection to be time matched with PK collection C4D8, C4D15: LFTs only

Procedure ^a	C	2 and	C3			C4			C5 to C17 ^b	ЕОТ	Follow- up (30 and 60 Days After Last Dose)	Follow- up (100 Days After Last Dose) ^C	Survival Follow-up ^d	Notes
	D1	D8	D15	D1	D2	D4 ^e	D8	D15	D1		(± 5 days)	(± 10 days)	(± 2 weeks)	
Thyroid Function Testing	x								X See note	х	X	X		Required for BMS-986183 and nivolumab combination therapy only. Free T3 and free T4 will be taken reflexively if TSH is abnormal. To be performed every other cycle after Cycle 3 (ie, Cycles 5, 7, etc). See Section 5.3.2.
Coagulation Panel	Х	Х	Х	Х			Х	Х	Х	Х	X	X		See Section 5.3.2
Troponin T or I														As clinically indicated
ECHO or MUGA									C5 only	X				At other times as clinically indicated
Tumor Biopsy (Fresh)	See assessment schedules in Section 5.6.1 for details.												C2, 24 to 48 hours post dose and at any other time an investigator chooses to obtain a biopsy during the study period. See Section 3.3.1 for further details.	
Viral biomarkers (for HCV and HBV)	X			x					Х	X	X	X		For HCV infected, HCV RNA on treatment For HBV infected, HBV DNA on treatment
Pregnancy Test	Х			Х					Х	Х				See Table 5.1-1

Procedure ^a	C	2 and	C3			C4			C5 to C17 ^b	ЕОТ	Follow- up (30 and 60 Days After Last Dose)	Follow- up (100 Days After Last Dose) ^c	Survival Follow-up ^d	Notes
	D1	D8	D15	D1	D2	D4 ^e	D8	D15	D1		(± 5 days)	(± 10 days)	(± 2 weeks)	
Concomitant treatments	Х	Х	X	Х	Х	Х	Х	Х	Х	Х	X ^g	Х		See Table 5.1-1
Adverse Event Reporting		1	1						1	L				
Monitor for Nonserious Adverse Events	X	х	x	X	X	Х	X	Х	X	Х	X	X		See note in Table 5.1-1.
Monitor for Serious Adverse Events	X	Х	x	X	X	Х	X	Х	X	Х	X	X		See note in Table 5.1-1.
PK and Immunogenicity	Asse	essme	nts S	ee Se	ctior	n 5.5.			•					
Biomarker Assessments	See S	lection	n 5.6.											
Efficacy Assessments														
Tumor Assessment		Att	the sta	art of there	°Cyc after	le 3 an $(\pm 1 \text{ works})$	d the eek)	en Q6	W,	Х	x ^h	x ^h	x ⁱ	Scans must be de-identified. See Sections 5.3.1, 5.4.1
Clinical Drug Supplies		-							-					
BMS-986183 Administration	X			x					X					The start and stop time of the study drug infusion should be documented (start of drug infusion = 0 hour). See Section 4 for administration details.
Nivolumab Administration	x			X					X					For BMS-986183 and nivolumab dose escalation (Part 3) and BMS-986183 and nivolumab dose

Procedure ^a	C2	2 and	C3		C4					ЕОТ	Follow- up (30 and 60 Days After Last Dose)	Follow- up (100 Days After Last Dose) ^c	Survival Follow-up ^d	Notes
	D1	D8	D15	D1	D2	D4 ^e	D8	D15	D1		(± 5 days)	(± 10 days)	(± 2 weeks)	
														expansion (Part 4) only. BMS-986183 is infused first followed by nivolumab. See Section 4 for administration details. See Section 3.1.1.2 for observation times. The start and stop time of the study drug infusion should be documented (start of drug infusion = 0 hour).
Other														
Other Anti-cancer Therapies													x ^j	
Subject Status													X	Also see tumor assessment schedule above

^a In the event that multiple procedures are required at a single timepoint, the ECG may be obtained up to 15 minutes earlier, vital signs may be obtained up to 10 minutes earlier or later, and clinical laboratory sample may be obtained up to 5 minutes earlier than the nominal PK timepoint, ensuring the PK samples can be collected on time.

^b Individual subjects with SD or PR may have 6 months (9 cycles, with 21 days/cycle) of extended treatment with BMS-986183 after the first treatment period (17 cycles, with 21 days/cycle) on a case-by-case basis after specific consultation and agreement between the investigator and BMS medical monitor. These subjects, as well as any subjects in BMS-986183 and nivolumab dose escalation (Part 3) or BMS-986183 and nivolumab dose expansion (Part 4) who meet the criteria to continue combination therapy beyond progression (see Section 4.5.7), will follow the assessment/procedure schedule for C5 to C17 subjects.

^c BMS-986183 and nivolumab dose escalation (Part 3) and BMS-986183 and nivolumab dose expansion (Part 4) only.

^d For all subjects, subject status will be assessed by telephone contact, office visit, or documented clinic visit every 12 weeks (± 2 weeks) up to 6 months from his or her last dose of study drug.

^e C4D4: ± 1 day.

f

Vital signs will be obtained before the BMS-986183 infusion and then every 30 minutes (\pm 10 minutes) until 30 minutes following completion of the last infusion. If any vital sign is abnormal at the final check, the subject must be observed further for a period of time, as clinically indicated. The start and stop time of the study drug infusion should be documented (start of drug infusion = 0 hour).

^g Only anti-cancer treatments.

^h Only at the 60-day follow-up visit (BMS-986183 dose escalation [Part 1] or BMS-986183 dose escalation [Part 2]) or the 100-day follow-up visit (BMS-986183 and nivolumab dose escalation [Part 3] or BMS-986183 and nivolumab dose expansion [Part 4]).

¹ Subjects with SD, PR, or CR at the EOT visit should undergo tumor assessment via CT/MRI scans at least every 3 to 4 months during the survival follow-up period (Section 3.1) until progression, death, or initiation of new treatment (whichever occurs first).

^J The nature and start dates of any new therapies during this period should be recorded. Only information related to subjects' survival and the start date of any subsequent therapies will be collected at these telephone contacts. Subjects who have progressed will be permitted to receive other anti-cancer therapies as appropriate, including investigational agents, during this follow-up period once the 60-day (BMS-986183 dose escalation [Part 1] or BMS-986183 dose escalation [Part 2]) or the 100-day follow-up visit (BMS-986183 and nivolumab dose escalation [Part 3] or BMS-986183 and nivolumab dose expansion [Part 4]) follow-up visit is completed.

C = cycle; D = day.

Procedure ^a	Day 0 b,c	C1 and Beyond D1	ЕОТ	FU (30, 60, and 100 Days after Last Dose) (30- and 60-day FU: ± 5 days)	Survival FU ^d (±2 weeks)	Notes
				$(100 - \text{day FU}: \pm 10 \text{ days})$		
Eligibility Assessments	1	1	T		-	r
Inclusion/Exclusion Criteria	X					Same criteria as in screening
ECOG	X	X				Refer to Appendix 5 and Section 3.3.1. For Day 0, must be within 14 days prior to treatment assignment.
Medical History	X					Interim history (medical, AE or SAE) that occurred during the survival FU period that was not previously reported.
Child-Pugh Score	Х					See Appendix 4 for scale.
Prior Treatments	X					Including prior cancer treatment regimens.
Safety Assessments						
Full PE	X	X				For Day 0, must be within 14 days prior to treatment assignment. If the screening full PE is performed within 24 hours prior to dosing on Day 1, then a single exam may count as both the screening and predose evaluation.
Targeted PE			Х	Х	X	See note in Table 5.1-1.
Physical Measurements	X	X	X	X		Height (Day 0 only), weight (for Day 0, must be within 14 days prior to treatment assignment).

Procedure ^a	Day 0 b,c	C1 and Beyond D1	ЕОТ	FU (30, 60, and 100 Days after Last Dose) (30- and 60-day FU: ± 5 days) (100-day FU: ± 10 days)	Survival FU ^d (±2 weeks)	Notes
Vital Signs ^e	X	X	X	X		Body temperature, blood pressure, and heart rate (if Day 0 and C1D1 coincide, record vital signs once).
ECGs	Х	X	X	Х		ECGs should be recorded after the subject has been supine for at least 5 minutes.
ECHO or MUGA	X		X			Must include a quantitative assessment of left ventricular ejection fraction and utilize the same modality for any subsequent assessments. ECHO/MUGA may be assessed up to 72 hours prior to the first dose. Also perform as clinically indicated.
Laboratory Tests	X	X	X	X		Day 0 laboratory values should be obtained within 14 days prior to the start of study drug. If the Day 0 laboratory tests are performed within 72 hours prior to dosing on Day 1 then a single exam may count as both the Day 0 and predose evaluation. Repeat the following if > 6 months since last treatment: hepatitis B surface antigen and hepatitis C antibody (if hepatitis C antibody is positive reflex to hepatitis C RNA) or hepatitis C RNA will be done at screening. Note: Testing for HIV-1 and HIV-2 must be performed at sites where mandated by local requirements.

Procedure ^a	Day 0 b,c	C1 and Beyond D1	ΕΟΤ	FU (30, 60, and 100 Days after Last Dose) (30- and 60-day FU: ± 5 days) (100-day FU: ± 10 days)	Survival FU ^d (±2 weeks)	Notes		
						Urine - Day 1 only, unless clinically indicated. See Section 5.3.2.		
Viral Biomarkers(for HBV and HCV)	Х	Х	Х	Х		For HCV infected, HCV RNA on treatment For HBV infected, HBV DNA on treatment		
Coagulation Panel	Х	Х	Х	Х				
Troponin T or I	Х					As clinically indicated		
Thyroid Panel including TSH, free T3, and free T4	Х	X See note				To be done Q6W. See Section 5.3.2.		
Pregnancy Test	Х	Х	Х	Х		For WOCBP only; see Section 5.3.2.		
PK and Immunogenicity Assessments See Section 5.5.								
Biomarker Assessments See Section 5.6.								
Tumor Assessment Tumor Imaging (See Section 5.3.1)	X		Х	X ^f	X ^g	Day 0 must be within approximately 30 days of C1D1. Then at the start of Cycle 3 and then Q6W thereafter (± 1 week). Scans must be de-identified. See Section 5.3.1.		
Concomitant Treatments	Х	Х	Х	X ^h		Medications administered within 4 weeks of dosing and all antiviral medications taken for any length of treatment 100 days after the last dose of study drug.		

Procedure ^a	Day 0 b,c	C1 and Beyond D1	ЕОТ	FU (30, 60, and 100 Days after Last Dose) (30- and 60-day FU: ± 5 days) (100-day FU: ± 10 days)	Survival FU ^d (±2 weeks)	Notes		
Adverse Event Reporting				(100 uuy 1 0. 2 10 uuys)				
Clinical Complaints		Х				See note in Table 5.1-1; only if subject entered survival FU.		
Monitor for Nonserious Adverse Events		X	X	X		From first dose of study drug until a total of 100 days post discontinuation of dosing or subject's participation in the study if the last scheduled visit occurs at a later time. See Section 5.3.		
Monitor for SAEs	Х	Х	X	Х		From the time of consent until a total of 100 days post discontinuation of dosing. See Section 5.3.		
Clinical Drug Supplies								
Dose Level Assignment	X					At the completion of Day 0 procedures and eligibility determined.		
BMS-986183 Administration		X				The start and stop time of the study drug infusion should be documented (start of drug infusion = 0 hour). See Section 4 for administration details. Subjects in BMS-986183 dose escalation (Part 2) Combination Therapy Extension Option must receive their first dose of combination therapy within 6 weeks of their last study drug administration.		

Procedure ^a	Day 0 b,c	C1 and Beyond D1	ΕΟΤ	FU (30, 60, and 100 Days after Last Dose) (30- and 60-day FU: ± 5 days) (100-day FU: ± 10 days)	Survival FU ^d (±2 weeks)	Notes	
Nivolumab Administration		X				BMS-986183 is infused first followed by nivolumab. See Section 4 for administration details. See Section 3.1.1.2 for observation times. The start and stop time of the study drug infusion should be documented (start of drug infusion = 0 hour). Subjects in BMS-986183 dose escalation (Part 2) Combination Therapy Extension Option must receive their first dose of combination therapy within 6 weeks of their last study drug administration.	
Other							
Survival FU					X ⁱ		

^a In the event that multiple procedures are required at a single timepoint, the ECG may be obtained up to 15 minutes earlier, vital signs may be obtained up to 10 minutes earlier or later, and clinical laboratory sample may be obtained up to 5 minutes earlier than the nominal PK timepoint, ensuring the PK samples can be collected on time.

Abbreviations: C = cycle, D = day; FU = follow=up; PE = physical examination; T3 = triiodothyronine; T4 = thyroxine; TSH = thyroid stimulating hormone.

^b Day 0 is first day of assessment for either retreatment or combination therapy extension.

^c For BMS-986183 dose expansion (Part 2), BMS-986183 and nivolumab dose escalation (Part 3), and BMS-986183 and nivolumab dose expansion (Part 4), if the Day 0 and C1 visits occur on the same day, then only a single examination or procedure is needed.

^d Subjects will be followed up for up to 6 months after their last dose.

^e During C1: vital signs will be obtained before the BMS-986183 infusion and then every 15 minutes (± 5 minutes) until 60 minutes after completion of the infusion. After C1, vital signs may be obtained predose, every 30 minutes (± 10 minutes) until 30 minutes following completion of the infusion. If any vital sign

is abnormal at the final check, the subject must be observed further for a period of time, as clinically indicated. The start and stop time of the study drug infusion should be documented (start of drug infusion = 0 hour).

^f Only at the 60- and 100-day FU visits, unless discontinued for disease progression.

^g Subjects with SD, PR, or CR at the EOT visit should undergo tumor assessment via CT/MRI scans at least every 3 to 4 months during the survival FU period (Section 3.1) until progression, death, or initiation of new treatment (whichever occurs first).

^h Only anti-cancer treatments.

ⁱ Subject status will be assessed by telephone contact, office visit, or documented clinic visit every 12 weeks (± 2 weeks) up to 6 months from his or her last dose of study drug. The nature and start dates of any new therapies during this period should be recorded. Only information related to subjects' survival and the start date of any subsequent therapies will be collected at these telephone contacts. Subjects who have progressed will be permitted to receive other anti-cancer therapies as appropriate, including investigational agents, during this FU period once the 100-day FU visit is completed.

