All subjects will enter the safety follow-up period once the decision is made to discontinue the subject from treatment (eg, at end of treatment [EOT]).

After the EOT visit, all subjects will be evaluated for any new AEs for a total of 60 days after the last dose of study drug for BMS-986183 dose escalation (Part 1) and BMS-986183 dose expansion (Part 2) and for a total of 100 days after the last dose of study drug for BMS-986183 and nivolumab dose escalation (Part 3) and BMS-986183 and nivolumab dose expansion (Part 4). Follow-up visits should occur at 30 and 60 days (\pm 5 days) after the last dose. Subjects in BMS-986183 and nivolumab dose escalation (Part 3) and BMS-986183 and nivolumab dose expansion (Part 4) will have an additional visit at 100 days (\pm 10 days) after the last dose. All subjects will be required to complete their clinical safety follow-up visits regardless of whether they start new anti-cancer therapy, except those subjects who withdraw consent for study participation.

Subjects who develop toxicity requiring discontinuation of treatment will enter the safety follow-up period. The subject should be seen at least every 30 days, until the AE has resolved to baseline, stabilized, or been deemed irreversible.

Survival Follow-up Period

After completion of the safety follow-up period, all subjects will enter the survival follow-up period. All subjects will be followed by telephone contact, office visit, or documented clinic visit every 12 weeks (\pm 2 weeks) from his/her last dose of study drug for 6 months until progression or death. Both response and survival follow-up periods will occur simultaneously during the 6-month follow-up period. The duration of this period is up to 6 months following the subject's last dose of study drug. Subjects in the survival follow-up period who progress will be eligible to receive anti-cancer therapy as appropriate.

Retreatment during Survival Follow-up (Parts 3 and 4 only)

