Retreatment may be allowed in BMS-986183 and nivolumab dose escalation (Part 3) and BMS-986183 and nivolumab dose expansion (Part 4) of this study for subjects with disease progression during follow-up. Subjects who complete approximately 1 year (17 cycles, with 21 days/cycle) of study therapy and who enter survival follow-up with ongoing disease control (CR, PR, or SD) for reasons other than drug-related toxicity may be eligible for retreatment, upon subsequent confirmed disease progression within 12 months of the last dose of study drug (on a case-by-case basis) after careful evaluation and discussion with the BMS Medical Monitor to determine whether the benefit/risk ratio supports administration of further study therapy. Subjects meeting criteria for retreatment will be treated up to approximately 1 year (17 cycles, with 21 days/cycle) with the originally assigned dose regimen (eg, same dose and dose schedule administered during the first approximately 1 year [17 cycles, with 21 days/cycle]) or modified dose regimen, unless that dose and schedule were subsequently found to exceed the MTD, in which case the subject will be treated at the next lower or alternate dose and schedule. Subjects entering this phase will follow the schedule as outlined in Table 5.1-3. Samples for PK will be collected less frequently (Table 5.5.1-3).

Response Follow-up Period

Subjects with SD, PR, or CR at study drug discontinuation will continue to have radiologic and clinical tumor assessments at least every 3 to 4 months during the survival follow-up period (Section 3.1) until progression, death, or initiation of new treatment (whichever occurs first).

Radiological tumor assessments for subjects who have ongoing clinical benefit may continue to be collected after subjects complete the survival follow-up period of the study. Subjects who have disease progression following treatment with study drug will not be evaluated for response beyond the EOT visit and will be allowed to receive other tumor-directed therapy as required.

3.1.1 Dose Escalation (BMS-986183 Dose Escalation [Part 1] and BMS-986183 and Nivolumab Dose Escalation [Part 3])

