In BMS-986183 dose expansion (Part 2) only, subjects who have disease progression on BMS-986183 monotherapy will be able to receive combination treatment (their current BMS-986183 dose + flat dose of nivolumab, provided that this combination dose has been found to be safe from BMS-986183 and nivolumab dose escalation [Part 3]). This combination therapy option is not applicable during BMS-986183 dose escalation (Part 1). Eligible subjects may receive the combination option after careful evaluation and discussion with the BMS Medical Monitor to determine whether the benefit/risk ratio supports administration of further study therapy. Subjects meeting criteria for retreatment will be treated up to approximately 1 year (17 cycles, with 21 days/cycle) with a dose regimen of the combination of BMS-986183 and nivolumab dose escalation (Part 3). Such subjects must meet the eligibility criteria for receiving the combination of BMS and nivolumab as specified in Table 5.1-3.

If subjects in BMS-986183 dose expansion (Part 2) agree to receive the combination therapy, they must consent to a mandatory biopsy at clinically documented disease progression (see Section 3.3.1). In addition, subjects must wait at least 21 days since their last dose of BMS-986183 before receiving the combination therapy option, but they must receive their first dose of combination therapy within 6 weeks of their last study drug administration. These subjects will follow the assessment schedules in Table 5.1-3 and Table 5.5.1-3.

Subjects who agree to receive the combination therapy will be included in the main analysis up to and including disease progression. After disease progression, subjects who agree to receive the combination therapy will also be analyzed in a subanalysis.

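### Two schedule-table footnotes can be read as making progressed subjects wait for the 60- or 100-day visit before other anti-cancer therapy, a condition Section 3.1 does not impose

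*Protocol*

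**What the plan says.** **The footnotes.** Footnote j of Table 5.1-2 sits in the survival follow-up column, on the row for other anti-cancer therapies. It reads: "Subjects who have progressed will be permitted to receive other anti-cancer therapies as appropriate, including investigational agents, during this follow-up period once the 60-day" visit, or the 100-day visit for the combination parts, is completed. (It labels Part 2 as dose escalation; the 60-day visit is clearly meant for Parts 1 and 2.) Footnote i of Table 5.1-3, in the corresponding column, allows other therapies "including investigational agents, during this FU period once the 100-day FU visit is completed". Table 5.1-3 covers retreatment in Parts 3 and 4. It also covers Part 2 subjects who take the combination extension, of whom Section 3.1.2.1 says: "These subjects will follow the assessment schedules in Table 5.1-3".

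**Section 3.1.** The safety follow-up text says: "All subjects will be required to complete their clinical safety follow-up visits regardless of whether they start new anti-cancer therapy". The response follow-up text says that subjects who progress after study drug "will not be evaluated for response beyond the EOT visit and will be allowed to receive other tumor-directed therapy as required". The survival follow-up text says: "Subjects in the survival follow-up period who progress will be eligible to receive anti-cancer therapy as appropriate". None of these is tied to a visit.

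**Concomitant-treatment rows.** At the 30- and 60-day visits in Table 5.1-2 (footnote g), and at the 30-, 60- and 100-day visits in Table 5.1-3 (footnote h), the entry is limited to "Only anti-cancer treatments". The 100-day column of Table 5.1-2 has a plain X.

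**The concern.** A permission granted once a visit is completed reads as a condition: before the visit, the permission has not yet been given. Section 3.1 points the other way. Requiring safety visits whether or not new therapy has begun presupposes that new therapy can begin before those visits are finished.

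The subjects concerned have advanced HCC, have progressed and have stopped study drug. Sites work from the schedule tables, and Section 9.1.1 tells investigators not to depart from the protocol without approval except to remove an immediate hazard. A site that took the footnote literally could hold back next-line treatment, while one that followed Section 3.1 would not. No clause ranks the tables against the text. What is at stake is patient care and consistent conduct across sites.

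**Working it through.** The plan states no figure on this point, so there is nothing to reproduce. The check compares the texts, then works out the delay under a literal reading.

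**1. Does the order of the follow-up periods remove the conflict?** If survival follow-up always began after the last safety visit, the clause would only mark its start. The protocol gives three descriptions:
- Section 3.1, overview: safety follow-up is described together with simultaneous response and survival follow-up. It is unclear whether all three run together or only the last two.
- Section 3.1, Survival Follow-up Period: "After completion of the safety follow-up period, all subjects will enter the survival follow-up period". Yet contacts are timed every 12 weeks (±2 weeks) from the last dose. The first contact is at 12 × 7 = 84 days, range 84 − 14 = 70 to 84 + 14 = 98.
- Section 3.6: contacts run about every 12 weeks from the last follow-up visit. The first is at 60 + 84 = 144 days (Parts 1 and 2) or 100 + 84 = 184 days (Parts 3 and 4).

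The 60-day visit falls on days 55 to 65, so under either clock the first survival contact comes after it. The 100-day visit falls on days 90 to 110. On the last-dose clock the first survival contact (day 84) nominally precedes it by 16 days. In Parts 3 and 4 the clause can therefore have real effect inside survival follow-up as scheduled.

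**2. Delay under a literal reading.** Let V be the day of the required visit after last dose and t the days from last dose to the finding of progression, with study drug stopped. Then:

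wait = max(0, V − t)

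Inputs:
- V = 60 ± 5 or 100 ± 10 (Section 3.1).
- t = 0: progression found on a dosing day after the dose.
- t = 21: progression found when the next dose is due.
- t = 42: a scan at the 6-week limit on dose delay (Section 4.5.5). Scans stay on the first-dose clock whatever the dosing delay (Section 4.5.4).

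| t (days) | 60-day wording: nominal (window) | 100-day wording: nominal (window) |
|---|---|---|
| 0 | 60 (55–65) | 100 (90–110) |
| 21 | 60 − 21 = 39 (34–44) | 100 − 21 = 79 (69–89) |
| 42 | 60 − 42 = 18 (13–23) | 100 − 42 = 58 (48–68) |
| at or after the visit | 0 | 0 |

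The range is 0 to 65 days under the 60-day wording and 0 to 110 days under the 100-day wording. Section 3.1 implies no wait.

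**3. How many subjects?** Planned numbers are 30 + 50 = 80 in Parts 1 and 2 and 21 + 50 = 71 in Parts 3 and 4. Part 2 subjects who take the extension move to the 100-day wording. These are planned subjects, not affected ones. Only those who progress before the visit and have stopped study drug could be affected, and the documents do not allow that number to be derived.

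**The case against.** The best defence is scope. Both footnotes sit only in the survival column, refer to that follow-up period, and forbid nothing in words. Section 3.1 and Section 3.6 can be taken to place survival follow-up after the last safety visit, so the clause would simply say when the period opens. Section 3.1 answers the question for the safety period, and Section 3.4.3 restricts drugs given with BMS-986183 without setting a wait after it stops. The principle in Section 2.3 that subjects' welfare comes first also favours Section 3.1.

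Much of this stands. The milder reading is plausible, and strongest for Parts 1 and 2, where survival contacts fall after the 60-day visit on either clock. It is not conclusive: the clause does not say it is a period marker, the parallel sentence in Section 3.1 omits it, and the 84-day contact precedes the 100-day visit. If the clause is only a marker, it is redundant and can go at no cost.

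Two stronger inferences are tempting and should not be drawn:
- **That the protocol prohibits next-line therapy for 60 or 100 days.** It does not; Section 3.1 expressly allows it.
- **That the tables contradict themselves because they collect anti-cancer treatments at the safety visits.** Recording a treatment is not permitting it, and subjects who have not progressed may also start new therapy. In Table 5.1-2 the restriction does not extend to the 100-day column. These rows are weak corroboration only.

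**Conclusion.** The point holds as an ambiguity. Read literally, the two footnotes conflict with Section 3.1 on when a progressed subject may start other anti-cancer therapy. The possible delay runs from 0 to about 65 days (60-day wording) or 110 days (100-day wording), depending on when progression is found. These figures assume a literal reading, visits kept within their windows, and a subject off study drug. Combination subjects treated beyond progression, and those retreated or on the extension, are not affected while they remain on study therapy. The documents do not show that any site would read the footnotes this way.

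No estimate, sample size, power or error rate changes, and no bias is claimed. The correction is worth making because it is cheap and protects access to treatment.

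**What to change.** In footnote j of Table 5.1-2, delete the clause making permission depend on completion of the 60- or 100-day visit. In footnote i of Table 5.1-3, delete the matching clause for the 100-day visit. In both, add: after progression and discontinuation of study drug; safety follow-up visits continue per Section 3.1. Nothing more is needed, since both footnotes already require the nature and start date of new therapy to be recorded.

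The cost is one clause in each of two footnotes, by amendment or administrative letter, with no new visits, data or subjects. There is one small downside: some adverse events in the 60- or 100-day window may arise under new therapy, and the window in SAP Section 6.1.2 does not close when that therapy starts. Section 3.1 already accepts this. The recorded start dates would allow such events to be flagged in the adverse-event listing, as an optional addition.
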